Inclusion criteria: women aged 18-40, defined as metabolically healthy ($n = 18$) or insulin resistant ($n = 18$) based on insulin sensitivity (Si) values ("insulin resistance" defined as $Si < 1.61 \times 10^{-4}$; healthy as $Si > 1.89 \times 10^{-4}$ ($\text{min}^{-1} \times \mu\text{U}^{-1} \times \text{mL}^{-1}$); calculated by minimal model assessment of glucose tolerance test, based on the median of the non-diabetic population^{87,88}), and body mass index (BMI = weight (kg) / height² (m²)) between 18 kg/m² and 35 kg/m². Women with mild or moderate depressive symptoms not meeting the criteria for Major Depressive Disorder will be included.

Exclusion criteria: men, left handed, acute medical illness, uncorrected thyroid disease, diabetes (fasting glucose ≥ 126 mg/dL), neurological disease, major depression, substance abuse, claustrophobia or MRI contraindications (pacemakers, pumps, or metallic agents or devices), severe calorie restriction, intense physical exercise ≥ 1 hour/day, smoking within 6 months, hormonal, insulin sensitizing, or centrally acting medications within 2 months, pregnancy within 6 months, lactation, cardiac or pulmonary insufficiency, liver or renal insufficiency ($>2.5 \times$ normal transaminases levels, plasma creatinine ≥ 1.4 mg/dL), history of lactic acidosis, BMI ≥ 35 kg/m², and opioid allergy.

b. Recruitment Plan and Study Design

i. Number of Subjects

We plan to enroll 36 women aged 18-40, defined as metabolically healthy (n = 18) or insulin resistant (n = 18). We expect to perform initial clinical screening assessments on 60 women to achieve our target enrollment. We will replace drop outs with new subjects to complete studies on 36 subjects.

ii. Method of Contact

Women will be recruited through news boards, websites, UMClinicalStudies Registry, the Reproductive Endocrinology Clinics, and from the Investigational Weight Management study, a study of phenotypic influences on weight loss and metabolic function in normal and obese individuals, conducted by [name] at the Michigan Nutrition and Obesity Research Center (MNORC) in the Michigan Metabolomics and Obesity Center (MMOC). Participants enrolled in this study may choose to participate in the proposed project, and have been evaluated for general health, mood, physical fitness, body composition, and metabolic, metabolomic, and hormonal phenotyping.

iii. Method of Consent

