1	
Visit 1 will occur at the Michigan Clinical Research Unit (MCRU), and will last approximately 4-5 hours.
 
Obtain informed consent and medical, neurological, and psychiatric histories. Perform structured diagnostic interview to rule out current clinical Major Depression or other psychiatric diagnoses^{88,90}.
 
Clinical assessment: collect initial clinical measures and confirm eligibility for continued participation. Assay samples collected after overnight fast. Clinical measures: thyroid stimulating hormone (TSH), comprehensive chemistry panel (CCP), blood counts, and a glucose tolerance test. Samples will also be obtained for hormonal and metabolic measures, pending eligibility. Additional samples will be collected and stored for future investigation of potential biomarkers for comorbid metabolic and mood dysfunction.
 
Anthropomorphic measurements: measure height, weight, and sizes for BMI and waist-to-hip ratio and circumference calculations.
 
Eligibility for continued enrollment in study will be determined from these assessments. If enrolled, glucose tolerance results will also be used to calculate baseline glucose, insulin, and insulin resistance measures.
 
Assessment of affective and mood state: state measures include the Positive and Negative Affect Schedule (PANAS)⁹¹, Profile of Mood States (POMS)⁹², State portion of the Spielberg Anxiety Inventory (STAI)⁹³, and Snaith-Hamilton Pleasure Scale measure of anhedonia⁹⁴. Trait measures include the Trait portion of the STAI, Beck Depression Index (BDI)⁹⁵, Patient Health Questionnaire-9 (PHQ-9)⁹⁶ and depression and anxiety subscales of the NEO Personality Inventory (NEO-PI-R)⁹⁷.
 
Cognitive assessment: measures of cognitive function may include California Verbal learning Test – Second Edition (CVLT-II; verbal memory), Controlled Oral Word Association (COWA; verbal fluency), and Brief Visual Memory Test – Revised (BVMFT-R; visual memory).

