[name] will prescribe medication and supervise monitoring during treatment. If subjects have minor side effects, the dose escalation may be slower. Women will be maintained in the study if they can at least reach a dose of 1000 mg/day. Treatment will be monitored by phone calls to the subjects at 2 week intervals throughout each treatment arm.

Treatment will be coordinated through the Investigational Drug Services (IDS) in the University of Michigan Department of Pharmacy. IDS will manage treatment-related details including randomization and blinding, drug and placebo acquisition and compounding, medication storage and dispensing, treatment compliance, accountability records, and adherence to regulatory requirements.

4	Clinical (except histories, TSH, CCP, and blood count), anthropomorphic, and affect and mood assessments, similar to Visit 1.
5	PET scan, similar to Visit 3, but consisting of a single baseline PET scan without the stress challenge scan.
6	MRI scan, similar to Visit 2, may be performed depending on funding availability.

Four week medication-free wash-out period between treatment arms

Begin 2nd treatment arm: participants begin the 2nd arm of 16 weeks metformin or placebo treatment.

Dosing and medication details identical to those described for 1st treatment arm; *treatment will be coordinated through the IDS*

7	Clinical, anthropomorphic, and affect and mood assessments, similar to Visits 1 and 4.
8	PET scan, similar to Visits 5.
9	MRI scan, similar to Visit 2, may be performed depending on funding availability.

Clinical measures: clinical assessments of metabolic and endocrine environment to determine overall status at each of the time points and to assess response to treatment. Metabolic measures include a 2 hour 75g oral glucose tolerance test, with samples collected at -30, -15, 0, 30, 60, 90, and 120 minutes. Anthropomorphic measures will also be collected to control for changes in affective state that may be attributed to change in body composition. Sample collection and clinical assays will be performed at the MCRU and associated core laboratories.

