Potential subjects will be informed that becoming a participant in this study is entirely by their own free choice. Subjects may drop out of the project by their own free will, after having agreed to become a subject. They may refuse to enroll in this project, or drop out of this project without any penalty. By doing so, participants will not lose any benefits that they are entitled to. Subjects will be asked to discontinue their participation if they no longer meet criteria, did not comply or the investigator no longer thought it was safe for the subject to be involved with the study.

- ii. If a subject withdraws prior to completion, what is the plan for the use of their data

Subjects who have withdrawn prior to the completion of the study and have provided usable data in terms of the study's criteria will be included in the final analysis. Incomplete data sets which will not add any meaningful material for the research goals will not become part of the analysis.

8) Identifiable Data

- a. Indicate how subjects are identified in research records

Subjects will be indirectly identified in research records: personal identification (e.g. name, phone number, SSN, medical record number) will be replaced with coded identifiers in study databases. Coding will be kept secured and stored separately from study data.

- Explain the necessity for collection or maintaining data linked to subjects' identities.

Contact information for each will be collected and maintained in order to inform the subject of any necessary or pertinent information about the study prior to or following their participation. Also contact information such as mailing addresses are needed in order to mail the subject a packet of information about the study prior to their involvement. Name or medical record numbers may be used to confirm medical histories with subject permission.

- How long will the identifiers be retained?

Identifiers will be retained for 2 years following the final publications associated with the study, or when at least 2 years have elapsed since the formal discontinuation of the study.

9) Data Retention and/or Data Destruction Plan

- i. How long will you keep subject data?
- ii. If you plan to destroy the data, how will you destroy it?

Data collected will be retained for study recordkeeping purposes and for future research use. Data will be destroyed after 15 years by deleting the electronic files and shredding the paper documents.

10) Risks & Benefits

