Pain stressor challenge: the stressor challenge that will be used for this protocol consists of moderate levels of sustained deep muscular pain, achieved by infusing medication-grade 5% hypertonic saline into the relaxed masseter (jaw) muscle. Infusion is controlled by a computerized pump, through which participants maintain a pain intensity level of 40/100 via an electronic visual analog scale. Participants may experience physical or emotional discomfort during the challenge, however we will ensure that they are aware of the level of pain they will experience and that they understand the scale ratings of pain and internal states and can use them in a reliable manner.

Metformin/placebo side effects: metformin is in the biguanidine class of anti-diabetic drugs, and regulates hepatic gluconeogenesis, with secondary action enhancing glucose uptake at peripheral tissues through increased transport across the cell membrane. While metformin is not recognized as a true insulin sensitizing agent, it has been shown to improve insulin resistance and reduce fasting and postprandial insulin concentration, and has benefits over the thiazolidinedione class of drugs in terms of weight gain, improvements in lipid, vascular, and inflammatory profiles, and does not induce hypoglycemia even in non-diabetic individuals. Side effects of metformin include abnormal liver

changes, lactic acidosis and the more common side effects of gastric distress, nausea and vomiting. All subjects will be monitored for possible side effects such as nausea, vomiting, diarrhea, anorexia, and abdominal discomfort. These side effects tend to be mild, dose-related and improve with continued use of metformin. GI side effects will be minimized using a low dose of medication titrated slowly over a three-week period. Hypoglycemia is rare and tends to occur in the setting of alcohol abuse or prolonged starvation. Malabsorption of vitamin B₁₂ and folate occurs with long-term treatment, although it usually does not lead to anemia. Non-hormonal contraception will be recommended.

B) Discuss they the risks to the subjects are reasonable in relation to the anticipated benefits

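### Visit 4 drops the chemistry panel, so no scheduled test can check the protocol's own liver and kidney limits before the second treatment arm (minor patient-safety point)

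*Combined protocol and SAP*

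**What the plan says.** Four parts of the protocol bear on this.

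- **Exclusion criteria.** Liver or renal insufficiency is excluded. The limits are transaminases more than 2.5 times normal and a creatinine threshold: "normal transaminases levels, plasma creatinine ≥ 1.4 mg/dL), history of lactic acidosis".
- **Subject Withdrawal.** The criteria are carried past entry: "Subjects will be asked to discontinue their participation if they no longer meet criteria".
- **Visit table.** Visit 1 lists "thyroid stimulating hormone (TSH), comprehensive chemistry panel (CCP), blood counts, and a glucose tolerance test". Visit 4, after the first 16-week arm, reads "Clinical (except histories, TSH, CCP, and blood count), anthropomorphic, and affect and mood assessments, similar to Visit 1". Next come a PET scan, an optional MRI and a "Four week medication-free wash-out period between treatment arms". The second arm then starts: "Dosing and medication details identical to those described for 1st treatment arm". Visit 7, after the second arm, reads "Clinical, anthropomorphic, and affect and mood assessments, similar to Visits 1 and 4".
- **Risks & Benefits.** "Side effects of metformin include abnormal liver" is the start of a sentence that goes on to list liver changes, lactic acidosis and gastrointestinal effects.

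Monitoring during treatment consists of a phone call every two weeks, supervision by the prescriber, and attention to symptoms. None of these is described as including a blood test.

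**The concern.** The protocol chooses numerical liver and kidney limits, says that women who cease to meet criteria should stop, and names a liver effect of the drug. It then omits the one listed test that could show whether a limit has been crossed.

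Two groups are affected differently. Women randomized to placebo first meet metformin for the first time in the second arm, on an old result. Women randomized to metformin first finish the drug with no scheduled look at the liver. A woman who had crossed a limit without symptoms since Visit 1 would not be found by any scheduled test before the second arm. What is at stake is participant safety; no estimate or test in the Statistical Design section depends on it.

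**Working it through.** The plan gives no figure for the age of the panel, so there is nothing to reproduce. The check walks through the visit table and adds the intervals.

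**Inputs**
- First arm 16 weeks, wash-out 4 weeks, second arm 16 weeks (visit table).
- 18 insulin-resistant women (Number of Subjects). Order is assigned by permuted blocks (Drug treatment paragraph). About 9 women per order is an assumption of balance.
- The CCP is taken to supply transaminases and creatinine. This is an inference: it is the only listed test that could.

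**Where a chemistry panel is scheduled**

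| Point in study | Panel scheduled? |
|---|---|
| Visit 1 | Yes |
| Visits 2 and 3 (MRI, PET) | None listed |
| First arm, 16 weeks | None listed; phone calls |
| Visit 4 | Expressly omitted |
| Visits 5 and 6 (PET, optional MRI) | None listed |
| Wash-out, 4 weeks | None listed |
| Start of second arm | None listed |
| Visit 7 | Unclear: Visit 1 has the panel, Visit 4 does not |

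Scheduled panels between Visit 1 and the start of the second arm: 0, for all 18 women.

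**Placebo first (about 9 women).** Let g be the time from Visit 1 to the first dose of the first arm, which the protocol does not state. The age of the panel at the first metformin tablet is g + 16 + 4 = 20 + g weeks, so at least 20. If g is assumed to lie between 1 and 8 weeks, the range is 21 to 28 weeks.

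**Metformin first (about 9 women).** From the last metformin tablet to Visit 7 is 4 + 16 = 20 weeks at the least. If Visit 7 includes the CCP, that is their first scheduled panel after metformin. If Visit 7 follows the Visit 4 exception, there is none. On either reading there is no panel at the end of metformin.

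**With a panel at Visit 4.** The result would be about 4 weeks old when the second arm starts, or somewhat more if Visits 5 and 6 delay the wash-out. All 18 completers, instead of 0, would have a scheduled panel between Visit 1 and the second arm. With Visit 7 also settled, all 18 would have a panel after each treatment; as written, none do on either reading.

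**The case against.** **The omission is a deliberate choice.** The exception is written out in an approved protocol, and the limits are entry criteria judged at Visit 1. The withdrawal sentence is general and does not order re-testing; taken as such an order, it would require thyroid function to be repeated too. This stands in part. The plan is not in breach of its own rules, and how often to repeat safety tests is a clinical judgement. But the protocol ties a liver effect to the study drug, which it does not do for the thyroid.

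**The risk may be small.** Placebo-first women take no active drug during the gap, so only background change could move them past a limit. They are aged 18 to 40, non-diabetic and screened. For metformin-first women, the check before the second arm precedes placebo. All of this stands. The documents give no rate of crossing the limits and do not say that a 20-week-old panel is too old. A reader might infer that women are knowingly started on metformin in an unsafe state; nothing in the documents supports that.

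**Other safeguards exist.** They include slow titration, symptom monitoring, two-weekly calls, a 24-hour number, physician oversight, withdrawal on the investigator's judgement and adverse-event reporting. A reader might infer that safety is unmonitored, which would be wrong. The prescriber may order tests at any time. The narrower point survives, because none of these safeguards schedules a transaminase or creatinine value.

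**Part of the protocol was not available.** The text between the Study Team Expertise section and the eligibility criteria could not be read, and monitoring duties might be described there. This is a reason to lower confidence.

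**Conclusion.** The point holds as a minor patient-safety improvement, with moderate confidence. In the text available, 0 of 18 insulin-resistant women have a scheduled panel between Visit 1 and the second arm. About half start metformin on a result at least 20 weeks old, and the other half finish metformin with no scheduled liver check.

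It rests on three assumptions: that the CCP carries transaminases and creatinine, that order is roughly balanced, and that the unavailable text adds no test. It concerns scheduled tests only.

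Two further inferences should be resisted. One is that Visit 1 holds the only panel of the whole study: Visit 7 may include one, though too late to inform the second arm. The other is that the blood count should also return at Visit 4. It has no bearing on the liver and kidney limits, and the Risks & Benefits section links the vitamin malabsorption to long-term treatment and describes anemia as an unusual result.

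**What to change.** 1. At Visit 4, take the CCP out of the exception, leaving histories, TSH and blood count as the items not repeated. Draw it with the glucose tolerance samples, of which seven are already timed at that visit.
2. At Visit 7, state that the CCP is included.
3. Before the second arm is dispensed, have the prescriber compare every woman's Visit 4 transaminases and creatinine with the exclusion limits, blind to treatment order, and repeat an out-of-range value.
4. Report any woman who does not enter the second arm for this reason, with her treatment order.

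**Cost.** About 18 × 2 = 36 panels for 18 completers, slightly more if drop-outs are replaced. Only the 18 at Visit 4 are certainly new, since Visit 7 may already intend the panel. Both are existing laboratory visits, so the routine panels need no extra visit. Repeating an out-of-range value does need an occasional extra draw and may briefly delay the second arm.

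There is also a design cost. A woman whose value stays out of range may be lost from the second arm. If metformin caused the change, that loss depends on treatment order, which matters in a crossover of 18; hence step 4. The change does not detect problems in mid-arm and does not address lactic acidosis.

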As the frequency of metabolic disorders increases (including type II diabetes, the metabolic syndrome, and insulin resistance), associated co-morbidities are also becoming more prevalent. A relationship between metabolic dysfunction and mood disorders, including depression, is well-documented, and individuals with an underlying metabolic disorder represent a population with high risk of developing depression. While the mechanisms underlying the relationship between insulin metabolism and mood dysregulation remain largely unexplored, the endogenous opioid system, acting through μ -opioid receptors, has separately documented regulatory roles in both insulin metabolism and mood regulation, and our preliminary data suggests a role in mediating their relationship. We propose to evaluate central μ -opioid system function (in the amygdala and nucleus accumbens, motivation and affect-regulating regions) and mood/affective state in insulin-resistant (defined by low insulin sensitivity) women. We will evaluate women after placebo and metformin treatment in a randomized cross-over study design, with baseline comparison to a sample of healthy control women. We will approach this investigation using metabolic assessment of insulin and endocrine function, neuropsychological assessment of affective and mood state, fMRI, and PET imaging with a selective μ -opioid receptor radiotracer to quantify 1) μ -opioid receptor availability *in vivo* (binding potential, BP_{ND}) at baseline, and 2) endogenous opioid release in response to a standardized stress challenge known to induce the release of endogenous opioids. We hypothesize that metabolic and mood symptoms in women with non-diabetic metabolic dysfunction, reflected by insulin resistance, will be associated with reduced μ -opioid receptor-mediated neurotransmission and alterations in fMRI activation patterns during emotional processing.

Aim 1: establish the relationships between insulin resistance, affective state, and μ -opioid system function.

Aim 2: examine the effects of insulin regulation on μ -opioid system function and affective state after 16 weeks of metformin treatment in insulin-resistant women.

Aim 3: determine whether identifiable differences can be observed in emotional processing between insulin resistant women compared to normal controls using validated functional MRI tasks.

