basis into tracer transport (K_1 ratio) and receptor-related BP_{ND} parametric maps, co-registered to each other. PET images will be co-registered to the T1-weighted MR structural, anatomical image, affine transformed and warped to standard MNI stereotactic space using mutual information algorithms¹⁰⁰. Inclusion of the pain challenge in a separate scan will allow comparison of pain and baseline conditions at the same timepoint in relation to tracer administration. The reduction in BP_{ND} from baseline to stress challenge provides a measure of endogenous opioid release in response to the stressor (related to the occupancy and endogenous ligand-receptor interactions)^{48,49}. The stress challenge scan will occur after the baseline scan to avoid carry-over effects from active to baseline states, as previously described^{50,101}.

MRI: structural, anatomical, and functional images will be acquired using a 3T whole-body magnetic resonance imaging scanner with a head coil. Images will be acquired axially with a three-dimensional, volumetric acquisition. Functional images will be collected during a presentation of words or images with an affective valence (positive or negative) or affectively neutral. Images may also be collected during validated tasks of verbal processing (women must decide whether presented words are written in upper or lower case letters, or if they have abstract or concrete word meaning) and visual memory (women must determine which of two test patterns matches the stimulus pattern).

Drug treatment: the University of Michigan Investigational Drug Service (IDS) will manage and coordinate metformin and placebo treatment. Metformin is the most widely prescribed drug for type 2 diabetes, and while generally not recognized as a true insulin sensitizing agent, it has been shown to improve insulin resistance and reduce fasting and postprandial insulin concentration without hypoglycemia. [name] will provide medical oversight and prescribe treatment medication. After baseline assessments, IDS will randomize participants to the order in which they receive metformin or placebo using a randomly permuted block design. Investigators and participants will be blinded to treatment order randomizations. Placebo pills will look identical to metformin pills but contain no active ingredients, and will be taken on an identical schedule as the active drug.

v. Survey Instruments

1. What are they?

- 1) Positive and Negative Affective Scale (PANAS)

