PET imaging analysis: PET image data of 1) μ -opioid receptor BP_{ND} and 2) opioid release in response to stress challenge, calculated as the difference in BP_{ND} between baseline and challenge conditions, will be analyzed using Statistical Parametric Mapping software (SPM8, Wellcome Department of Cognitive Neurology, London, UK) with 1) volume-of-interest (VOI) analyses and 2) whole-brain statistical parametric mapping. VOIs will be defined using Montreal Neurological Institute (MNI) coordinates in affect/mood regulating regions (amygdala, nucleus accumbens, and rostral anterior cingulate). BP_{ND} values for these regions will be extracted for outlier assessment and further analyses in SPSS (SPSS Inc, Chicago, IL) or SAS (SAS Institute Inc, Cary, NC). In a separate set of analyses, whole-brain statistical parametric maps will be created for comparisons which do not assume selective involvement of specific regions, but will only include regions with specific μ -opioid receptor binding.

A global model based on the general linear model (GLM) will also be used to compare relationships between metabolic measures and mood/affective state, and to determine potential interactions and control for variables (e.g., age, BMI, estradiol and testosterone plasma levels) that could potentially confound the relationship between insulin resistance and mood state or opioid system activity.

6. Spinler SA. Challenges associated with metabolic syndrome. *Pharmacotherapy.* Dec 2006;26(12 Pt 2):209S-217S.
7. Hosler AS. Prevalence of self-reported prediabetes among adults participating in a community-based health awareness program, New York State. *Prev Chronic Dis.* Apr 2009;6(2):A48.

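### Controlling affect for change in body composition would put a post-randomisation covariate into the Aim 2 metformin-placebo comparison, unless the plan labels that analysis as secondary

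*Combined protocol and SAP*

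**What the plan says.** Aim 2 concerns mu-opioid function and "affective state after 16 weeks of metformin treatment in insulin-resistant women". The design is given under Specific Aims: "We will evaluate women after placebo and metformin treatment in a randomized cross-over study design". The Drug treatment paragraph fixes the timing: "After baseline assessments, IDS will randomize participants to the order in which they receive metformin or placebo".

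The visit table schedules body measurements together with affect and mood scores at Visit 4, after the first arm, and again at Visit 7, after the second: "Clinical, anthropomorphic, and affect and mood assessments, similar to Visits 1 and 4". The Clinical measures paragraph below the table describes the clinical assessments as serving "to determine overall status at each of the time points and to assess response to treatment", and then adds: "Anthropomorphic measures will also be collected to control for changes in affective state that may be attributed to change in body composition".

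Section 12, Statistical Design, describes a general linear model that relates metabolic measures to mood and affect. It is also meant to "control for variables (e.g., age, BMI, estradiol and testosterone plasma levels) that could potentially confound the relationship between insulin resistance and mood state" or opioid activity. It does not say whether BMI is the baseline or an end-of-arm value, and it writes out no metformin-placebo contrast, adjusted or unadjusted.

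**The concern.** Metformin against placebo is the only randomised comparison in the study. Its strength is that the difference in affect between a woman's two arms can be attributed to the drug, apart from period and carry-over effects. A covariate measured at the end of each arm may itself have been changed by the drug. Conditioning on it has two consequences:

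- Any effect of metformin on affect that runs through body composition is removed, so the result is not the total effect.
- If body composition and affect share some other cause, their association can appear as a drug effect, or hide one.

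The documents make a route possible without measuring it. The risk section says "All subjects will be monitored for possible side effects such as nausea, vomiting, diarrhea, anorexia, and abdominal discomfort", and such symptoms could move both body composition and affect. The protocol does not say whether the adjusted result would be the main or a supporting one, so the choice could be made after seeing both.

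**Working it through.** **Where the control falls.** Healthy controls have no repeat studies (Method of Interaction/Procedure/Intervention), so a change in body composition exists only in the 18 randomised women. Randomisation follows the baseline visits, and Visits 4 and 7 follow treatment. Within a woman, a baseline value is the same for both arms, so its main effect cancels from the metformin-minus-placebo difference. Body composition can therefore alter the Aim 2 estimate only through the end-of-arm values.

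**No figure to reproduce.** The available text states no effect size, SD, alpha or power for Aim 2. What follows is an illustration on assumptions.

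**Inputs.** From the protocol: 18 insulin-resistant women and two arms. Assumed:

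- 9 women per sequence, two-sided 5% test, and a period term in both models.
- rho = 0.7, the within-woman correlation of affect between arms.
- A total effect of 0.5 SD of the affect score.
- d, the mean metformin-placebo shift in end-of-arm body composition, in SDs of its within-woman difference. For example, 0.5 would be a 1 kg shift with a 2 kg SD.
- r, the within-woman correlation between the body-composition and affect differences.

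**Unadjusted contrast.** The SD of the affect difference is sqrt(2(1 - 0.7)) = 0.775. The noncentrality is 0.5/0.775 x sqrt(18) = 2.74 on 16 degrees of freedom, which gives 73% power. The false-positive rate is 5%.

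**Adjusted contrast.** The body-composition difference enters uncentred, as an end-of-arm covariate does in a within-woman model (15 degrees of freedom). The expected estimate is effect - r x d x 0.775. With r = 0.3:

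- d = 0.25: 0.5 - 0.3 x 0.25 x 0.775 = 0.44
- d = 0.5: 0.5 - 0.3 x 0.5 x 0.775 = 0.38
- d = 0.8: 0.5 - 0.3 x 0.8 x 0.775 = 0.31

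With r = -0.3 the same terms are added. Power and error rates come from 100,000 simulated trials per setting:

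| d | False-positive rate, r = 0.3 | Estimate and power, r = 0.3 | Estimate and power, r = -0.3 |
|---|---|---|---|
| 0 | 5% | 0.50 SD, 74% | 0.50 SD, 74% |
| 0.25 | 6% | 0.44 SD, 61% | 0.56 SD, 80% |
| 0.5 | 8 to 9% | 0.38 SD, 43% | 0.62 SD, 81% |
| 0.8 | 12% | 0.31 SD, 25% | 0.69 SD, 78% |

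The false-positive column assumes that metformin has no effect on affect and that r arises from other causes.

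**Sensitivity.** At r = 0.2 the false-positive rate is 5 to 8% over d = 0.25 to 0.8. At r = 0.5 it is 8%, 17% and 28% at d = 0.25, 0.5 and 0.8. At d = 0.5 and r = 0.3, with rho = 0.5, 0.7 and 0.8, power falls from 51, 73 and 88% to about 24, 43 and 63%.

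**What the adjusted number estimates.** If r arises only because body composition affects affect, the adjusted figure is the effect of metformin not passing through body composition. If r arises partly from an unmeasured common cause, it is neither that nor the total effect.

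**The case against.** The strongest reply is that the sentence explains why data are collected and specifies no model. It names no covariate form, contrast or outcome score, and controlling could mean a covariate, stratification, a mediation analysis or a sensitivity check. This stands. A reader might infer that the plan commits its main Aim 2 result to this adjustment; the documents do not say so.

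A reader might also take the covariate list in section 12 as confirmation. It is weak support, because that model is described for associations between metabolic measures and mood or opioid activity. BMI and hormones are legitimate covariates there and in the baseline comparison with controls.

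Nor should the missing treatment contrast be read as a wrong method. A within-woman comparison is the natural reading of the design, so its absence from section 12 is missing detail. The pages between the study-team section and the eligibility criteria were also not available for this check.

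The study's objective is mechanistic, and separating weight-related from insulin-related change in affect fits it. This justifies keeping the adjusted analysis, but does not make it the estimate of what metformin does to affect.

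Finally, the harm needs a metformin-placebo shift in body composition that the documents do not quantify. Their remarks on weight and appetite compare metformin with thiazolidinediones, and the risk section describes the gastrointestinal effects as usually mild and lessening over time. This too stands, and is why the figures are a range starting at no harm.

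**Conclusion.** The point holds in a limited form. The text states an intention that, if followed in the main Aim 2 affect analysis, conditions the randomised comparison on a variable metformin may have altered. With no shift in body composition the adjustment does no harm and can slightly help precision. At r = 0.3 and shifts of 0.25 to 0.8 SD, the false-positive rate rises to about 6 to 12%. A 0.5 SD effect is understated by up to 0.19 SD or, with the opposite sign of r, overstated by the same amount. It would be wrong to conclude that the adjustment always weakens the drug effect: in the opposite-sign case the estimate is inflated, and power is about 78 to 81% against 73%. All these sizes rest on assumed values of d, r and rho. The baseline comparison with controls and the Aim 1 associations are not affected. Minor.

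**What to change.** Add a short paragraph to section 12:

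- The main Aim 2 analysis of each affect score is the within-woman metformin-minus-placebo contrast at the end of each 16-week arm, with a period term and no post-randomisation covariate.
- The version adjusted for change in body composition is reported beside it as a named secondary, mechanistic analysis. Its assumption is stated: body composition and affect share no unmeasured common cause.

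The sentence under Clinical measures can then point to that secondary analysis. The change costs wording only. It needs no new visits or data, the adjusted analysis is kept, and the period term uses one degree of freedom (about 0.3 percentage points of power if there is no period effect).
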